9.2.2 Study Subjects

All meningococcal cases reported during the above mentioned timeframe(s) will be included in both parts of the study (descriptive and analytical). Data from the national surveillance on meningococcal disease, as well as vaccination status of the cases, will be collected through PHE in England.

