9.2.3 Study Population Selection

The study population for the descriptive part of the study is the general population in England. Individuals will be included in the cohorts targeted for vaccination in England. Exploratory analyses could be envisioned for other regions (Northern Ireland, Wales, Scotland), if data become available.

Inclusion Criteria

Case definitions are given in section 9.4.2. Final criteria for 4CMenB failure will depend on the schedule for use of 4CMenB in the population. The design of the study will also affect inclusion criteria, e.g. for case-control study controls will be included as defined in section 9.5.

Exclusion Criteria

Excluded will be those who have not been offered the vaccine (e.g. immigrants) and individuals who were not vaccinated according to the NIP (partially vaccinated). From previous vaccine studies, we know that the proportion partially vaccinated will be low (PHE personal communication).

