9.4 Data Sources

Exposure of interest

Data for this study will be collected through the national surveillance system, as well as an additional source(s) to collect data regarding vaccinations. All cases of confirmed MenB disease will routinely be followed up to obtain vaccination history (including batch number) through enhanced surveillance by PHE. Additionally, demographics and medical history will be ascertained.

For the analytical study the screening method will be used. As above, vaccine history of confirmed cases will be collected to assess the proportion of cases that were fully vaccinated (PCV).

The comparator will be national vaccination rates as the proportion population vaccinated (PPV). These data may for instance be taken from the Cover Of Vaccination Evaluated Rapidly (COVER) system which collects data about the coverage of routine infant vaccination from health authorities in England, and/or from a general practice database [Anon, 1999]. COVER data would have some limitations as it only provides coverage at fixed time points (12, 24 months) and we would not know about partial vaccination. Data will therefore be supplemented by disaggregate data obtained from either general practice or child health database to provide estimates of dose specific coverage at specific ages.

Outcomes of interest

The study will be partnered with Public Health England (PHE) and its Meningococcal Reference Unit (MRU) in England, so that national laboratory surveillance data for meningococcal disease can be used [Gray SJ et al., 2006]. PHE's national surveillance system consists of statutory reporting of confirmed invasive meningococcal disease by laboratories. Statutory notification by physicians to local units of PHE ensures rapid follow up of clinically diagnosed cases and helps to ensure complete laboratory investigation. Clinical specimens and isolates of *Neisseria meningitidis* are also referred for capsular group specific PCR and routine serogrouping and subtyping.

In addition, all isolates referred to MRU from individuals eligible for vaccination will have qualitative and quantitative assessment of meningococcal antigens (Meningococcal antigen typing system or MATS) will be evaluated for each case where the organism is identified by culture. For cases with PCR-only confirmation of capsular group B (no

GSK Vaccines S.r.l.		Observational Study Protocol V72_38OB
03 SEP 15 Version 3 Final	Confidential	Page 31 of 61

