Our analyses will only include individuals in England fully and timely vaccinated according to the routine, standard national immunization schedule as described in section 9.3.1. Exploratory analyses could be envisioned such as for other schedules (e.g. catch-up at 3,4,12 months or 4,12 months), capsular non-B, other regions (Wales, Scotland), if data become available.

Following these definitions, please find a flowchart with the meningococcal case identification process and case definitions below (Figure 5).

Depending on results, fulfilling case definition A or B (or none of these)

**** Only capsular group B (case definitions A or B) or none of these NB: vaccine failure: A or B, and appropriately vaccinated at least 14 days before

9.4.3 **Operational Variable(s) Definition**

See above under 9.3.3 and 9.4.2.

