9.7.3 Statistical Methods

For each of the proposed study designs, the statistical methods are as follows:

1. Descriptive (no hypothesis testing):

This study will provide a summary of the epidemiology of all capsular groups of meningococcal disease, e.g. by vaccination status, age, setting and method. The method will be purely descriptive and summarise the observed number of *N. meningitidis* cases reported to PHE, stratified by variable of interest. More details are described above.

2. Analytical study:

Vaccine effectiveness (VE) is generally defined as the % reduction in the attack rate in vaccinated compared with unvaccinated children in the same birth cohorts. VE will be assessed by the screening method, or by a case-control method if the screening method cannot be used (for example, if appropriate coverage data cannot be determined).

a. Screening method:

For this method, the VE can be estimated using the formula below, where PCV is the proportion of cases that are vaccinated and PPV is the proportion population vaccinated (coverage):

$$VE = 1 - (\underline{PCV \times (1-PPV)})$$
$$((1-PCV) \times PPV)$$

The vaccine effectiveness estimate will be calculated along with the 95% confidence interval using the exact binomial distribution for the proportion of cases vaccinated in each of the study settings.

b. Case-control method:

In case-control studies, vaccine effectiveness is based on the odds ratio (OR) and is defined as: VE = 1 - OR

The vaccine effectiveness estimate will be calculated along with the 95% confidence interval using the standard errors from logistic regression.

If it is decided to pursue a case-control method, for instance if uptake information is difficult to obtain, the three controls for each case would as a minimum be matched on age (same month of birth if that is sufficient to define vaccine eligibility for infants) and sex.

As mentioned earlier, additional calculations can be considered to investigate the doseresponse relationships for each antigen in the vaccine (versus having at least one antigen, as described in the secondary objective).

As the number of cases due to other capsular groups is expected to be too small for analysis within the study period, at a later stage, outside the scope of this study protocol, it could be envisioned to evaluate both cross protection against other capsular groups and any capsule replacement after introduction of the vaccine.

Subgroup analyses

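### Section 9.4.2 admits only fully vaccinated individuals to the analyses, which removes the unvaccinated cases that the effectiveness estimate needs

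*Protocol*

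**What the plan says.** The protocol describes who enters the effectiveness analysis in several places.

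- **9.4.2, repeated under Definitions in the abstract (section 4):** "Our analyses will only include individuals in England fully and timely vaccinated according to the routine, standard national immunization schedule". The next sentence moves catch-up schedules, non-B capsular groups and other regions to possible exploratory analyses.
- **9.2.2:** "All meningococcal cases reported during the above mentioned timeframe(s) will be included in both parts of the study (descriptive and analytical".
- **9.2.3, with the same exclusion in the abstract:** people who were not offered the vaccine are excluded, and so are "individuals who were not vaccinated according to the NIP (partially vaccinated". The section also refers to the cohorts targeted for vaccination.
- **9.3.2:** the primary outcome is confirmed capsular group B disease.
- **9.4:** "vaccine history of confirmed cases will be collected to assess the proportion of cases that were fully vaccinated (PCV".
- **9.7.3:** VE is the percentage "reduction in the attack rate in vaccinated compared with unvaccinated children in the same birth cohorts". In the screening formula, "PCV is the proportion of cases that are vaccinated and PPV is the proportion population vaccinated (coverage".
- **9.5:** the worked example counts unvaccinated cases explicitly, through the term 119 × 10%.

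**The concern.** Both estimators rest on a contrast between vaccinated and unvaccinated. The screening formula uses the odds PCV/(1 − PCV), so the number of unvaccinated cases admitted determines the answer. A rule that admits only vaccinated individuals removes that quantity. The sentence in 9.4.2 is therefore a stated rule that cannot be followed, and not a detail left for an analysis plan. Section 9.2.2 pulls the other way: its wording admits cases of any age and any capsular group to the analytical part. The two sentences cannot both hold, and neither matches 9.7.3. Since 9.7.3 also says that the screening method allows no control for confounding, the definition of the case set is one of the few safeguards the primary estimate has.

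**Working it through.** **Inputs.** Coverage (PPV) 90%, VE 60% and 175 cases (9.5, Table 1). At age one, 119 observed cases per year (9.5). Under age one, 210 observed cases per year, 5/12 of them below 5 months, with VE 0% below 5 months and 50% at 5 to 12 months (9.5). Expected group B cases at all ages over three years: 1895 (Table 3). Formula (9.7.3): VE = 1 − [PCV/(1 − PCV)] × [(1 − PPV)/PPV]. At PPV = 0.9 the last factor is 1/9.

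**1. The plan's own figure.** PCV = PPV(1 − VE)/(1 − PPV × VE).
- At VE 60%: 0.36/0.46 = 0.7826.
- At VE 40%: 0.54/0.64 = 0.8438.
- n = 1.96² × 0.7826 × 0.2174/(0.8438 − 0.7826)² = 174.8 with unrounded inputs, so 175 as in Table 1.

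The other 15 cells of Table 1 reproduce in the same way. The planned PCV of 78% means that about 22% of the planned cases are unvaccinated.

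**2. The set that 9.7.3 needs (age one, per year).**
- Vaccinated: 119 × 0.9 × 0.4 = 42.84. Unvaccinated: 119 × 0.1 = 11.9. Total 54.74, which the protocol rounds to 55.
- VE = 1 − (42.84/11.9)/9 = 1 − 3.6/9 = 60%, the planning value.

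**3. 9.4.2 as written.**
- Vaccinated 42.84, unvaccinated 0, so PCV = 1. The denominator (1 − PCV) × PPV is 0 and VE is undefined.
- If the population is restricted in the same way, 1 − PPV is also 0 and the ratio is 0/0.
- In the case-control fallback no unexposed subject remains, so the odds ratio cannot be estimated.

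**4. 9.2.2 taken alone.** All 1895 cases are set against 90% coverage. The result depends on who is counted as vaccinated:

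| Counted as vaccinated | Number | PCV | VE |
|---|---|---|---|
| Age one, years 2 and 3 only | 85.7 | 4.5% | 99.5% |
| Age one, all three years (42.84 × 3) | 128.5 | 6.8% | 99.2% |
| The 128.5, plus 5 to 12 months (210 × 7/12 × 0.9 × 0.5 × 3 = 165.4) | 293.9 | 15.5% | 98.0% |
| The 293.9, plus under 5 months at 90% (210 × 5/12 × 3 × 0.9 = 236.3) | 530.1 | 28.0% | 95.7% |

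**5. Why the catch-up cohorts need a rule.** An unvaccinated case follows no schedule and can be assigned to one only by date of birth. Suppose vaccinated catch-up cases are set aside and unvaccinated ones are kept. Let f be the ratio of unvaccinated catch-up cases to unvaccinated routine cases. Then VE = 1 − [3.6/(1 + f)]/9 = 1 − 0.4/(1 + f). The protocol gives no value for f. Assuming f = 0.10 to 0.25, a true 60% would read as 64% to 68%.

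**The case against.** The strongest reply is that 9.4.2 was meant to say which schedule counts as vaccinated. The sentence follows the definition of vaccine failure and precedes a contrast with catch-up schedules. Read literally it gives a division by zero, which an analyst would see at once, so it could not silently produce a wrong published VE. The intended case set can also be assembled from other sections: targeted cohorts with the not-offered and partially vaccinated excluded (9.2.3), group B (9.3.2), and vaccinated against unvaccinated in the same birth cohorts (9.7.3). The PCV definition in 9.4 presupposes that some cases are not fully vaccinated.

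Most of this stands as an account of intent, and it rules out three stronger readings that a reader might infer.

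- **That the study would report a VE near 99%.** This needs 9.2.2 to be applied alone. Older children and adults are removed as not offered the vaccine and as outside the targeted cohorts (9.2.3), non-B cases by the primary outcome (9.3.2), and cross-cohort comparison by 9.7.3. The figures in step 4 show what one sentence implies; they are not a forecast.
- **That 9.2.3 excludes unvaccinated children.** The words before the bracket could cover them, but the bracket limits the group to the partially vaccinated, and the next sentence speaks only of that group.
- **That the protocol nowhere gives the case set.** It does, but only in pieces.

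What does not stand is that 9.4.2 can be left as it is. It speaks of what the analyses include, it is followed by what is exploratory, and the abstract repeats it, so it reads as an analysis-set rule.

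**Conclusion.** The point holds for 9.4.2 and its repeat in the abstract: followed literally, the rule makes VE undefined under the screening method and inestimable under the case-control method, and it contradicts 9.7.3 and the example in 9.5. This needs no assumption beyond reading the sentence as written. The conflict between 9.2.2 and the other sections is one of wording. Its numerical consequence, a VE of about 96% to 99.5% at 90% coverage, would arise only if the restrictions elsewhere were ignored. The 64% to 68% for mishandled catch-up cohorts rests on an assumed f. Table 1 is correct for its own inputs; the error is in the population statements.

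**What to change.** Replace the sentence in 9.4.2 and in the abstract with one statement of the analysis set, for example:

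> The primary effectiveness analysis includes capsular group B cases in England whose date of birth places them in a cohort eligible for the routine standard schedule, either fully and timely vaccinated or unvaccinated; catch-up cohorts, vaccinated and unvaccinated alike, are exploratory.

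This keeps the restriction to timely vaccination and the exploratory status of catch-up that 9.4.2 already intends. In addition:

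- In 9.2.2, limit the inclusion of all meningococcal cases to the descriptive part, or make it subject to 9.2.3.
- In 9.2.3 and the abstract, reword the second exclusion so that it names only those who received some but not all doses due, and say that unvaccinated children in eligible cohorts are retained.
- State that the partially vaccinated are removed from both PCV and PPV. If they leave only PCV, they remain in 1 − PPV and the two odds no longer refer to the same groups.

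The cost is a wording amendment to 9.2.2, 9.2.3, 9.4.2 and the abstract. No extra cases are needed. Removing the partially vaccinated from PPV requires dose-specific coverage, which 9.4 already plans to take from general practice or child health data.

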9.4.4 Advisory Committee(s)

GSK Vaccines does not foresee the need for a Study Steering Group given PHE's expertise in vaccine effectiveness studies.

9.5 Study Size

a. Screening method

The number of cases required to estimate vaccine effectiveness with various levels of precision (based on the difference between the point estimate of VE and lower limit of the 95%CI) is shown in Table 1 below [Farrington CP, 1993]. Calculations assume 90% vaccine coverage in the populations and consider observed VE for 50% to 80%.

Table 1	Screening Method (Sample Size Calculation)
---------	--

Vaccine Coverage	Lower 95% CI limit below VE	Vaccine Effectiveness 50%	Vaccine Effectiveness 60%	Vaccine Effectiveness 70%	Vaccine Effectiveness 80%
	5%	3022	1742	882	361
90%	10%	874	516	271	117
2070	15%	445	269	145	65
	20%	284	175	97	45

If we assume 90% vaccine coverage and observe 60% vaccine effectiveness, then with 175 cases, the lower limit of the 95% confidence interval (CI) for vaccine effectiveness will be above 40%.

b. Case-control method

The number of cases and controls required (1:3 ratio) to estimate vaccine effectiveness with various levels of precision (based on the difference between the point estimate of VE and lower limit of the 95%CI) is shown in Table 2 below. The calculations assume 90%

GSK Vaccines S.r.l.		Observational Study Protocol V72_38OB
03 SEP 15 Version 3 Final	Confidential	Page 35 of 61

of controls are exposed to vaccine and consider observed VE for 50% to 80% [Schesselman JJ, 1982a], [Schesselman JJ, 1982b].

Table 2	Case-control Method (Sample Size Calculation for 1:3 matching)				
Probability of vaccination in controls	Lower 95% CI limit below VE	Vaccine Effectiveness 50%	Vaccine Effectiveness 60%	Vaccine Effectiveness 70%	Vaccine Effectiveness 80%
	5%	4900	2820	1428	585
90%	10%	1400	835	440	190
2070	15%	720	435	235	105
	20%	460	284	157	73

If we assume a vaccine exposure rate in the control population of 90% and observe 60% vaccine effectiveness, then with 284 cases and 852 controls (1:3 matching), the lower limit of the 95% confidence interval for vaccine effectiveness will be above 40%.

[figure not shown]
Expected numbers and feasibility

In order to calculate the expected number of cases after introduction of the 4CMenB vaccine in the UK, we need to take the currently observed number of cases and the vaccination status by age group into account. Figure 6 shows an assumed vaccination schedule by birth cohort for the years 2013, 2014 and 2015.

GSK Vaccines S.r.l.		Observational Study Protocol V72_38OB
03 SEP 15 Version 3 Final	Confidential	Page 36 of 61

Figure 6 Vaccination Status by Birth Cohort Over Time, UK

Potential situation at baseline: eligibility for vaccination in the first year of introduction of 4CMenB vaccine into the UK (e.g. from 1 January 2013):

Introduction of 4CMenB into NIP

From UK data presented at EMGM 2011, it is known that about 40% (5/12) of IMD cases below the age of one year occur in infants under 5 months of age. Taking into account that these children may not be well protected by the 4CMenB vaccine yet, the calculations use a VE of 0% at < 5 months of age. Similarly, for the ages 5 until 12 months of age, we assumed a slightly lower VE of 50%, while for all other ages the VE is assumed to be 60%.

GSK Vaccines S.r.l.		Observational Study Protocol V72_38OB
03 SEP 15 Version 3 Final	Confidential	Page 37 of 61

Potential situation after three years (e.g. at 31 December 2015): fully and partially (< 1 year of age) vaccinated birth cohorts:

Year 2013	1992	1993	1994	1995	1996	1997	1998	6661	2000	2001	2002	2003	2004	2005	2006	2007	2008	2009	2010	2011	2012	2013	2014	2015	
Year 2014	1992	1993	1994	1995	1996	1997	1998	1999	2000	2001	2002	2003	2004	2005	2006	2007	2008	2009	2010	2011	2012	2013	2014	2015	
Year 2015	1992	1993	1994	1995	1996	1997	1998	1999	2000	2001	2002	2003	2004	2005	2006	2007	2008	2009	2010	2011	2012	2013	2014	2015	

Fully vaccinated birth cohort

Partially vaccinated birth cohort

OBS-01 TEMP 01 / Atlas No. 295927 Version No. 2 / Version Date: March 30, 2015

┢

GSK Vaccines S.r.l.		Observational Study Protocol V72_38OB
03 SEP 15 Version 3 Final	Confidential	Page 38 of 61

From this schedule, using observed numbers of cases in the epidemiological year 1 July 2009 until 30 June 2010, the expected number of MenB cases for three years (2013, 2014 and 2015) has been calculated. Table 3 shows the expected numbers of meningococcal B cases after 4CMenB vaccination among infants and children in the United Kingdom assuming vaccine effectiveness of 60% and vaccine coverage of 90%.

Example: assuming a coverage of 90% (with 10% for unvaccinated) and VE of 60% in fully vaccinated infants between 12 and 24 months of age that currently have an observed number of 119 cases per year: (119*10%)+(119*90%*40%) = 55 expected cases per year. This age group is shaded in grey as an example in Table 3.

Table 3Observed and Expected Laboratory Confirmed Meningococcal
Capsular Group B Cases by Age and Epidemiological Year,
England & Wales, 2009-2010***

Observed # of cases	2009- 2010*	Birth cohort	Assumed age in 2013	2013	2014	2015	Expected # of cases	2013- 2015
< 1 year	210	2014				155	< 1 year**	465
1 year	119	2013			155	55	1 year	164
2 years	51	2012	< 1 year	155	55	51	2 years	153
3-4 years	66	2011	1	55	51	33	3-4 years	198
5-8 years	45	2010	2	51	33	33	5-8 years	135
9-10 years	13	2009	3	33	33	11	9-10 years	39
11-14 years	31	2008	4	33	11	11	11-14 years	93
15-19 years	77	2007	5	11	11	11	15 years	46
20-24 years	40	2006	6	11	11	11	16-20 years	96
25+	128	2005	7	11	11	7	20-24 years	107
NK	5	2004	8	11	7	7	25+	384
Total	785	2003	9	7	7	8	NK	15
		2002	10	7	8	8	Total	1895
*** 1 July 20 30 June 2010	09 -	2001	11	8	8	8		
		••••	10	0	0	0	**** 5-12	202
		2000	12	8	8	8	months	202
		1999	13	8	8	15		
		1998	14	8	15	7		
		1997	15	15	7	7		
		1996	16	7	7	7		
		1995	17	7	7	7		
		1994	18	7	7	4		
		1993	19	7	4	8		
		1992	20	4	8	8		
		1991	21	8	8	8		
		1990	22	8	8	8		
		1989	23	8	8			
		1988	24	8				

For the screening method, if we assumed 90% vaccine coverage and observe 60% vaccine effectiveness, then with 175 cases, the lower limit of the 95% confidence interval for vaccine effectiveness will be above 40%.

In conclusion, the study period may well take 3 years before we can draw final conclusions for the vaccine effectiveness of 4CMenB vaccination against meningococcal capsular group B-vaccine-type disease, in each specific age group.

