9.3 Variables

9.3.1 Exposure of Interest

GSK Vaccines' 4CMenB vaccine is used in this study as part of routine clinical care, e.g. as recommended in the NIP. Information on how the commercial product should be stored and administered is in accordance with applicable national or EU guidelines and is described in the package insert. Co-administration of other vaccines may occur as consistent with clinical practice.

Indication and schedule

The 4CMenB was registered in Europe in January 2013. The indication of the 4CMenB vaccine is for active immunisation against invasive disease caused by MenB strains in individuals from 2 months of age and older (3+1 schedule).

The anticipated schedule for 4CMenB in the UK is:

- 1. Infants standard routine at age 2, 4 with a booster at 12 months (2+1 schedule, 3 doses in total)
- 2. Infants for a NIP with small catch-up campaign, e.g. at age 3 and 4 months with a booster at 12 months (3 doses in total), or at 4 months with a booster at 12 months (2 doses in total)

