12.2 Publications

The final report will be provided by the above mentioned affiliations, and will be available within six months after the end of data collection for the analytical study. The actual date of the final report depends on a variety of factors, such as introduction of 4CMenB into the UK national immunisation schedule (expected Sep 2015), number of meningococcal cases reported and the subsequent power (precision of estimates) related to the analytical study. Based on sample size calculations, the expected total duration of the effectiveness study is 3 years, which would suggest a publication of the final report around early 2019.

Preparation of manuscripts based on PHE surveillance data will be by PHE.

A figure of the estimated timelines was included earlier in this protocol (Figure 4).

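### Table 3 does not follow the infant schedule or its stated birth-cohort basis: it understates total cases and overstates the vaccine-eligible cases usable for estimating effectiveness

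*Protocol*

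**What the plan says.** Section 9.3.1 gives the anticipated UK programme: "Infants standard routine at age 2, 4 with a booster at 12 months (2+1 schedule, 3 doses in total"), plus "Infants for a NIP with small catch-up campaign, e.g. at age 3 and 4 months with a booster at 12 months", or a shorter version from 4 months. No group older than infants appears in it.

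Section 9.5 bases the feasibility numbers on cohorts: "Figure 6 shows an assumed vaccination schedule by birth cohort for the years 2013, 2014 and 2015". The inputs are "vaccine effectiveness of 60% and vaccine coverage of 90" per cent, with no effect under 5 months, 50% from 5 to 12 months, "while for all other ages the VE is assumed to be 60" per cent. The table carries a column headed "Assumed age in 2013" and follows each birth cohort through three years. The surrounding text says that "Table 3 shows the expected numbers of meningococcal B cases after 4CMenB vaccination among infants and children in the United Kingdom"; the table's own title says England & Wales, 2009-2010.

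Section 9.5 then sets 175 cases (from Table 1) beside these counts and concludes that about three years may be needed, in each age group. Section 12.2 repeats this: "Based on sample size calculations, the expected total duration of the effectiveness study is 3 years". Section 9.4.2 restricts the analyses to people in England vaccinated fully and on time under the routine schedule, and counts routine-schedule failures from 14 days after the third injection. Section 6 starts data collection at programme launch, expected 1 September 2015.

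**The concern.** Read along its rows, Table 3 is not a cohort table:

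- Cohort 2011 is already aged 1 in the first programme year, so it was never eligible as infants. It still gets the vaccine reduction (55), then returns to the unreduced 51 and 33.
- Cohort 2012 is reduced under 1 (155) and at age 1 (55), then loses the effect at age 2 (51), against the stated 60% at all other ages.
- Cohort 1993 reads 7, 4, 8: the effect applies at ages 19 and 20 and vanishes at 21. No adolescent campaign is in section 9.3.1.
- Age 20 sits in both the 16-20 and the 20-24 row.

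Screening-method effectiveness can only be estimated from cases in cohorts that were offered the vaccine. If the table suggests more such cases than the programme will produce, the planned three years may give less precision than a reader of section 9.5 would expect.

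**Working it through.** **1. Reproduce the printed figures.** Coverage is 90%. The case multiplier is 0.10 + 0.90 × 0.40 = 0.46 at 60% effectiveness and 0.10 + 0.90 × 0.50 = 0.55 at 50%.

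- Under 1: 210 × 5/12 + 210 × 7/12 × 0.55 = 87.5 + 67.4 = 154.9 a year; × 3 = 465. The 5-12-month part is 3 × 67.4 = 202.
- Age 1: 3 × 119 × 0.46 = 164.
- Ages 16-20: 3 × 0.46 × (4 × 77/5 + 40/5) = 96.
- Ages 20-24: 3 × (4 × 8 + 8 × 0.46) = 107. Age 20 (3 × 8 × 0.46 = 11.0) is therefore in both rows.
- The rows sum to 1,895.
- Table 1: expected PCV = 0.36/0.46 = 0.7826. At a lower limit of 40%, PCV = 0.54/0.64 = 0.84375. So n = 1.96² × 0.7826 × 0.2174 / (0.84375 − 0.7826)² = 174.8, that is 175.

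Everything reproduces. Apart from the age-20 overlap, the fault lies in the programme that was modelled.

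**2. Same annual grid, effect carried by cohort, infants only.** Change in total cases:

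- age 1 in year 1 unreduced: 119 − 54.7 = +64.3
- ages 16-20 unreduced: 208.8 − 96.0 = +112.8
- age 2 in year 3 reduced: 51 × 0.54 = −27.5
- age 20 counted once: −11.0

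Total: 1,895 + 138.6 = about 2,034.

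Cases carrying a vaccine effect in Table 3: 202 + 164 + 96 = 462. By cohort: 202 (5-12 months) + 2 × 54.74 = 109 (age 1) + 51 × 0.46 = 23 (age 2) = 335 before rounding of the parts. From age 1 upwards: 109 + 23 = about 132.

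**3. Roll-out inside the 36 months.** Assume eligibility for those aged up to 2 months at launch, constant births, and cases spread evenly within each age band. At age a months (2 or more), eligible cohorts are present for 38 − a of the 36 study months, so the mean eligible time is:

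| Age | Mean eligible time | Expected cases |
|---|---|---|
| 5-12 months | 29.5/12 = 2.458 years | 210 × 7/12 × 0.55 × 2.458 = 166 |
| 1 year | 20/12 = 1.667 years | 119 × 0.46 × 1.667 = 91 |
| 2 years | 8/12 = 0.667 years | 51 × 0.46 × 0.667 = 16 |

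Pooled from 5 months: about 273 (298 with the catch-up cohort). Total cases in all persons: about 2,094 (2,069 with catch-up).

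**4. Fully vaccinated analysis.** From the 12-month dose: 91 + 16 = 107. Starting 14 days later removes 54.74 × (0.5/12) × (25.75/12) = 4.9 cases, leaving about 102. With catch-up: about 116-120.

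Lower limit at 60% effectiveness, Table 1 method, n = 107: upper PCV = 0.7826 + 1.96 × √(0.7826 × 0.2174/107) = 0.861, so the limit is 1 − (0.861/0.139)/9 = 31%. The exact binomial interval (section 9.7.3), evaluated at the expected PCV, gives 34%.

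| Cases | Table 1 method | Exact |
|---|---|---|
| 102 | 30% | 33% |
| 107 | 31% | 34% |
| 132 (annual grid) | 36% | 37% |
| 175 | 40% | 41% |

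**5. Time to 175 cases.** Replace 38 − a by T + 2 − a, for T months of study.

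- Age 1 alone: 54.74 × (T − 16)/12 = 175 gives T of about 54 months.
- 5-12 months alone: 67.4 × (T − 6.5)/12 = 175 gives about 38 months (36 with catch-up).
- From the 12-month dose, at T = 46: 136.9 (age 1) + 35.2 (age 2) + 7.6 (age 3) = 180, or 173 with the 14-day lag; hence about 46 months.
- Pooled from 5 months: about 28 months.

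**The case against.** A reader might infer that Table 3 simply overstates the case counts. It does not: it tabulates cases in all persons, and those rise once the unplanned reductions are removed. At age 1 the all-person count becomes 119 + 54.7 + 54.7 = about 229 against the printed 164. Only the count of vaccine-eligible cases falls.

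A reader might also infer that the 175 is wrong, or that three years fails altogether. The 175 comes from Table 1, is conditional on its inputs and reproduces. The protocol names no Table 3 row as the basis for three years, and the table already printed 164 at age 1, below 175. Pooling from 5 months gives about 273 cases, ample by count. At the blended effectiveness, though, the pooled limit is not above 40% either. Underlying cases are 166/0.55 = 301 and 107/0.46 = 232. Vaccinated cases are 0.9 × (301 × 0.5 + 232 × 0.4) = 219 and unvaccinated 53, so PCV = 0.804 and effectiveness is about 54%. The Table 1 method gives an upper PCV of 0.851 and a limit of about 36%. That is about 18 points below the estimate, inside the 20-point row.

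The shading of Figure 6 cannot be seen in the text at hand, and the figure may depict an older, wider programme. Section 9.7.4 calls the estimates rough and plans interim checks, section 9.9 warns about precision and declining disease, and no hypothesis is tested. These points stand. They lower the severity but do not remove the conflict with section 9.3.1 or the shortfall for the population that section 9.4.2 defines.

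**Conclusion.** The point holds as a should-fix. Table 3 contradicts the anticipated schedule and its own cohort basis, counts about 11 cases at age 20 twice, and mixes three geographies: the United Kingdom in the text, England & Wales in the counts, and England in the analysis. Total cases are understated (1,895 against about 2,034-2,094). Vaccine-eligible cases are overstated (462 against about 273-335).

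The three-year shortfall is established for two analyses only. The fully vaccinated analysis expects about 102-107 cases (132 on the annual grid), with a lower limit of about 30-34% (36-37%). Age 1 alone expects about 91-109. The 5-12-month group is borderline by count (166-202), and the pooled analysis from 5 months passes 175.

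These figures assume unchanged 2009-2010 rates, the protocol's coverage and effectiveness reached at once in eligible cohorts, on-time doses, and even spread of births and cases. Restricting to England, and the decline mentioned in section 9.9, would lower the counts further; the protocol gives no figure for either, so neither is included.

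**What to change.** - Reconcile Figure 6 and Table 3 with section 9.3.1, so that one programme underlies all three.
- Rebuild Table 3 by birth cohort for the September 2015 start, with the effect carried forward as each cohort ages.
- Remove the reduction at ages 16-20 unless the schedule includes that group, and count age 20 once.
- Use England counts, label them so, and show cases in vaccine-eligible cohorts separately from all cases.
- State which analysis group the 175 refers to, and give the expected cases and lower confidence limit at three years for that group. On present inputs this is about 102-107 cases and 30-34% for the fully vaccinated analysis. Adjust the duration statements in sections 9.5 and 12.2 to match.

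The cost is one recalculated table and a few sentences, with no extra subjects or data collection. The stated precision for the fully vaccinated analysis becomes less favourable.
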